## PROTOCOL SYNOPSIS

---

### **Open Label, Multinational, Multicenter, Real World Treatment Study of Single Agent AZD9291 for Patients with Advanced/Metastatic Epidermal Growth Factor Receptor (EGFR) T790M Mutation-Positive Non-Small Cell Lung Cancer (NSCLC) Who Have Received Prior Therapy with an EGFR Tyrosine Kinase Inhibitor (EGFR-TKI)**

---

#### **Objective**

The primary objective of this study is to assess the efficacy and safety of single agent AZD9291 in a real world setting in adult patients with advanced or metastatic, epidermal growth factor receptor (EGFR) T790M mutation-positive Non-Small Cell Lung Cancer (NSCLC), who have received prior EGFR-tyrosine kinase inhibitor (TKI) therapy.

#### **Study site(s) and number of patients planned**

Approximately 600 patients will be enrolled (dosed) in Europe. The recruitment will be increased beyond that as the study will expand in other regions of the world (America, Asia). Total recruitment for all regions (including China) is expected to be approximately 3500 patients, depending on recruitment speed and national reimbursement timelines

---

#### **Study period**

Estimated date of first patient enrolled	Q3 2015
Estimated date of last patient completed	Q2 2020*

---

\*depends on the date the last country obtains national reimbursement plus 90 days or 18 months after the last patient is enrolled.

#### **Study Design**

This will be an open-label, single-arm, multinational, multicenter, real world treatment study.

#### **Target patient population**

Adult patients (fulfilling the definition of “age of majority” per local regulations) with locally advanced (stage IIIB) or metastatic (stage IV) NSCLC with confirmed T790M mutation, who have received prior EGFR-TKI therapy.

### **Investigational product (IP), dosage, and mode of administration**

AZD9291 is an oral, potent, selective, irreversible inhibitor of both EGFR-TKI sensitising and resistance mutations in NSCLC with a significant selectivity margin over wild-type EGFR. AZD9291 will be administered orally as one 80 mg tablet once a day.

### **Duration of IP administration**

Patients may continue to receive AZD9291 as long as they continue to show clinical benefit, as judged by the investigator, and in the absence of discontinuation criteria (see section 4.3).

Enrolment will be closed within 6 months of market license approval in that country or at national reimbursement, whichever is sooner.

The study will be closed in each participating country as soon as possible following national reimbursement of AZD9291 in that country (up to a max of 90 days post reimbursement).

Patients withdrawing from the treatment prior to national reimbursement will be followed up as part of this study until death or lost to follow-up.

At national reimbursement patients still on treatment will be transitioned to commercial supply as long as the patient is benefitting from treatment as per investigator assessment, and in accordance with national regulations in the countries where the study is conducted.

In the event that national reimbursement should not be granted following a reasonable time after market license approval in the country, the study will be closed in a maximum period of 18 months after the last patient is enrolled in that country. Contingencies will be made locally to ensure continued drug supply for patients who are still deriving benefit from AZD9291 at that time.

If applicable, timelines for conversion to commercial drug will be agreed with local bodies which may include regulatory agencies, ethics committees, and institutions.

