### **4.4 Patient Withdrawal or Study Termination**

At any time, patients are free to discontinue AZD9291 treatment or withdraw from the study without prejudice to further treatment.

Reasons for withdrawal from the study:

- Eligibility criteria not fulfilled
- Death
- Withdrawal of consent.

If a subject wishes to withdraw their consent to both treatment and study assessments, they should be asked if they are willing to continue with survival follow-up (which can be conducted by telephone). If a subject wishes to withdraw their consent to further participation in the study entirely, including survival follow-up, this should be clearly documented in the subject notes and in the CRF.

The status of ongoing, withdrawn (from the study) and “lost to follow-up” subjects at the time of an overall survival analysis should be obtained by the site personnel by checking the subjects notes, hospital records, contacting the subjects general practitioner and checking publicly available death registries. In the event that the subject has actively withdrawn consent to the processing of their personal data, the vital status of the subject can be obtained by site personnel from publicly available resources where it is possible to do so under applicable local laws.

The withdrawal reasons must be documented and SAEs reported appropriately in the CRF. If the patient agrees, the investigator must follow the patient for safety reasons until 30 days post-last dose, and then for survival status (and also for progression status if the subject had not progressed). If patient declines, the investigator will separately follow up and manage any

SAEs as a matter of clinical practice. The patient or representative will return unused AZD9291 tablets.

AstraZeneca reserves the right to terminate the study. The study will be terminated if in the judgment of AstraZeneca, patients are placed at undue risk because of clinically significant findings or AZD9291 received national reimbursement.

The study will be closed in each participating country as soon as possible following national reimbursement of AZD9291 in that country (up to a max of 90 days post reimbursement). Enrolment will be closed within 6 months after market license approval in that country or at national reimbursement, whichever is sooner.

Patients withdrawing from the treatment prior to national reimbursement will be followed up as part of this study.

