At national reimbursement, patients still on treatment will be transitioned to commercial supply as long as patient is benefitting from treatment as per investigator assessment and in accordance with national regulations in the countries where the study is conducted.. Once the study is closed no further data will be collected. Reasons for termination or withdrawal must be documented in the CRF. All data, collected as part of the study, that is available at the time of discontinuation from treatment, withdrawal from study or study termination, must be recorded.

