#### 4.2.7 Efficacy

##### **Overall Survival (OS)**

Overall survival will be summarised using Kaplan-Meier (KM) estimates of the median time to death or censoring and quartiles together with their 95% confidence intervals. Kaplan-Meier estimates of the OS rate at appropriate time points (see Event rate at fixed time point) will be presented as well.

A plot of the KM OS curve will be produced, including tickmarks to identify censored observations and numbers of patients at risk.

The number of patients prematurely censored will be summarised. A patient would be defined as prematurely censored if moving to commercial supply or if their survival status was not defined at the date of study discontinuation and if his/her last available information in the CRF is more than 6 weeks prior to the study discontinuation.

In addition, duration of follow-up will be summarised:

- In censored patients who are alive at the last assessment before study discontinuation only: Time from date of first dose of AZD9291 in this study to date of censoring (date last known to be alive).
- In prematurely censored patients: Time from date of first dose of AZD9291 in this study to date of censoring.

- In all patients: Time from date of first dose of AZD9291 in this study to the date of death (i.e. overall survival) or to the date of censoring for censored patients.

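### The documents disagree on when survival follow-up ends; if patients off AZD9291 are observed longer than those moved to commercial supply, the Kaplan-Meier median OS would be biased low

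*Protocol*

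**What the plan says.** OS is the primary efficacy outcome (Protocol 2 and 9.5; SAP 1.3). Several passages bear on when its follow-up ends.

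- **Patients off drug.** Protocol Synopsis, Duration of IP administration: "Patients withdrawing from the treatment prior to national reimbursement will be followed up as part of this study until death or lost to follow-up". Protocol 4.4 has the parallel sentence without the closing words, "Patients withdrawing from the treatment prior to national reimbursement will be followed up as part of this study", and so does 10.2.4.
- **Patients on drug.** Same synopsis section: "At national reimbursement patients still on treatment will be transitioned to commercial supply as long as the patient is benefitting from treatment".
- **Country closure.** Protocol 4.4: "The study will be closed in each participating country as soon as possible following national reimbursement of AZD9291 in that country", with a ceiling of 90 days and no distinction by treatment status. The synopsis and 10.2.4 agree. Protocol 4.4 and 10.2.4 add: "Once the study is closed no further data will be collected".
- **SAP treatment of transitioned patients.** SAP 4.2.7: "A patient would be defined as prematurely censored if moving to commercial supply". These patients are counted and their follow-up time is summarised.
- **Censoring date.** SAP 3.1.1 censors survivors at study discontinuation. Protocol 9.2 uses the last date known alive. Neither gives a specific OS date for a patient who moves to commercial supply.
- **Survival checks.** Protocol 4.1 (Table 4, note g) and SAP 3.1.1 ask for survival status every 6 weeks to end of study. Protocol 4.4 also asks that vital status of ongoing, withdrawn and lost "subjects at the time of an overall survival analysis should be obtained by the site personnel".

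**The concern.** Kaplan-Meier assumes that a patient censored at a given time has the same subsequent risk of death as those who remain under observation. Under the synopsis rule, reimbursement splits patients by treatment status: those still benefiting leave the risk set, and those already off drug stay in it. If mortality is higher off drug, the remaining risk set is enriched with higher-risk patients and the survival curve falls too fast. More patients would not help, because this is bias and not sampling error.

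The precision of median OS is the only stated basis for the study size, and it assumes a 58-month study. The visible text sets no common OS cut-off and plans no analysis that tests or adjusts for commercial-supply censoring. The sensitivity analyses in SAP 2.2 concern protocol deviations.

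**Working it through.** **1. The passages side by side.** After a country closes, the until-death rule requires data on patients off drug, and the no-further-data rule forbids it. Both cannot apply. Three readings follow:

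- (a) patients off drug are followed to study end, and patients on drug are censored at reimbursement;
- (b) patients off drug are followed to closure, up to 90 days after reimbursement, and patients on drug are censored at transition;
- (c) everyone is followed to the same closure date.

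**2. The plan's own figure.** Protocol 9.5 gives 1983 events and a 95% CI of 23.9-26.1 months at N=3500 and median 25. With exponential OS, everyone followed to month 58, and accrual F(t) = (t/40)^k (k is not stated), solving for 1983 events gives k = 2.00. The same k returns 2197 and 2085 events at medians 21 and 23, as tabulated. CI: 25 × exp(±1.96/√1983) = 23.9 to 26.1. The half-width is 25 × 1.96/√1983 = 1.10 months; at median 21 it is 21 × 1.96/√2197 = 0.88.

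**3. Model for the three readings.** The following inputs are assumptions and are not in the documents.

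- Median time on drug T: 9.6 to 15 months. The low end borrows the preliminary median PFS in Protocol 1.2.
- Death hazard on drug, h_on: 0.005 or 0.012 per month.
- Reimbursement dates: spread over study months 20-58, 36-58 or 45-58.

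Patients leave drug, alive or dead, at rate a = ln2/T. They leave alive at rate λ = a − h_on and then die at rate h_off. So

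S(t) = exp(−a·t) + [λ/(a − h_off)] × [exp(−h_off·t) − exp(−a·t)],

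with h_off solved so that S equals 0.5 at the assumed median. Example with T = 9.6, h_on = 0.005 and median 25: a = 0.0722, λ = 0.0672, h_off = 0.0571, and S(25) = 0.164 + 4.45 × (0.240 − 0.164) = 0.50.

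**4. Results, true median 25 months** (200,000 simulated patients per scenario; Kaplan-Meier medians for reimbursement windows 20-58 / 36-58 / 45-58):

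| T, h_on, h_off | (a) Off drug to month 58 | (b) Full 90-day gap | (c) Common closure date |
|---|---|---|---|
| 9.6, 0.005, 0.0571 | 22.7 / 23.5 / 24.0 | 23.9 / 24.2 / 24.4 | 24.9 / 25.0 / 25.0 |
| 9.6, 0.012, 0.0490 | 23.3 / 23.9 / 24.3 | 24.2 / 24.5 / 24.6 | 24.9 / 25.0 / 25.0 |
| 15, 0.005, 0.0963 | 22.0 / 22.8 / 23.7 | 23.6 / 23.9 / 24.2 | 25.1 / 25.1 / 25.1 |
| 9.6, equal hazards 0.0277 | 25.2 / 25.1 / 25.1 | 25.3 / 25.2 / 25.1 | 25.2 / 25.1 / 25.1 |

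Over the unequal-hazard scenarios, reading (a) spans 22.0-24.3, a shortfall of 25 − 24.3 = 0.7 to 25 − 22.0 = 3.0 months. Reading (b) spans 23.6-24.6, a shortfall of 0.4 to 1.4. With true median 21 the spans are 18.8-20.4 and 19.7-20.7, shortfalls of 0.6-2.2 and 0.3-1.3. Measured against each run's simulated truth (up to 25.1), the largest shortfall under (b) is 1.5.

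**5. A shorter gap.** With T = 9.6 and true median 25, a full 90-day gap gave 24.0-24.5, a one-month gap 24.6-24.8, and a common date 25.0.

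**The case against.** A reader might infer that the plan, as written, stops survival follow-up for patients on drug, continues it for those off drug, and so yields a biased primary estimate. The documents do not support that. The until-death wording stands only in the synopsis. The closure rule applies to everyone, and Protocol 4.4 and 10.2.4 collect nothing afterwards. Following patients off drug to month 58 in a country reimbursed years earlier would breach those rules. Nor would bias survive every reconciliation: one closure date for all patients removes it.

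Other parts of the objection also stand.

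- Ninety days is a ceiling, and closure is to come as soon as possible. Transition may coincide with it.
- The SAP's prematurely-censored label is descriptive and fixes no censoring date. Its closing condition, last information more than 6 weeks before study discontinuation, may qualify transitioned patients too.
- Six-weekly survival status and the vital-status check could supply the missing data. The check does not name transitioned patients, however, and it sits against the no-further-data rule.
- Countries without reimbursement close within 18 months of last enrolment, with no split at reimbursement.
- Direction needs higher mortality off drug. That is plausible but not given. Treatment beyond progression is allowed, and some patients stop for toxicity or by choice.

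The study is also descriptive, with no hypothesis tests. What remains is that no passage guarantees a common date, and SAP 4.2.7 points to transition as an early end of OS observation.

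**Conclusion.** The concern holds in conditional form and should be fixed. The defect is an unreconciled contradiction on the end of OS follow-up that permits censoring by treatment status. It is not an established bias in the primary estimate.

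With true median 25 months, the median would be low by about 0.7-3.0 months if patients off drug are followed to study end, and by about 0.4-1.4 months for a full 90-day gap (0.3-1.5 over true medians of 21 and 25, measured against simulated truth), less if the gap is shorter. The first range is mostly at or above the stated half-width of about 1.1 months. The second reaches it only in the less favourable scenarios. With a common date or equal hazards there is no bias.

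These sizes rest on assumed reimbursement dates, time on drug and hazards. At median 25 the assumed off-drug hazard is between 0.0490/0.012 = 4 and 0.0963/0.005 = 19 times the on-drug hazard. A weaker contrast would shrink the bias, so the low ends are not floors.

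**What to change.** 1. Reconcile the synopsis (Duration of IP administration) with Protocol 4.4 and 10.2.4 on when survival follow-up ends. Protocol 5 also needs aligning, since it lists discontinuation of AZD9291 as an end of follow-up.
2. In SAP 3.1.1 and 4.2.7, set one OS cut-off per country, the country closure date, for all patients regardless of treatment status. Reconcile the SAP's study-discontinuation censoring with the last-known-alive rule in Protocol 9.2.
3. Record survival status of transitioned patients up to that date, using the six-weekly follow-up and the vital-status check already in the protocol.
4. If that status cannot be obtained, add a sensitivity analysis that censors every patient in the country at the transition or reimbursement date. Making that the primary analysis would discard more deaths than necessary.
5. Show OS with unequal follow-up only as supplementary, and declare the change in SAP section 6, which now reports none.

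The cost is SAP wording, one derived date per country, and the deaths of patients off drug after closure. CI width scales with 1/√events. In the unequal-hazard scenarios at median 25, moving from reading (a) to a common closure date changes the event fraction from 0.542 to 0.523 at the mildest (√(0.542/0.523) = 1.02) and from 0.457 to 0.365 at the most costly (√(0.457/0.365) = 1.12), so the interval widens by about 2-12%. A second set of assumed scenarios gave 4-11%. The precision table should also be restated, because it follows everyone to month 58 and so allows for no early country closure.

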### **Study measures**

Data collected will include patient demographics, information needed to determine patient eligibility (including medical history, past and current disease characteristics, and tumor EGFR mutational status), AZD9291 exposure (including starting dose, dose adjustments or discontinuations), investigator-reported efficacy (including tumor response and disease progression), overall survival (OS), and safety (including serious adverse events [SAEs], adverse events leading to dose modification, and adverse events of special interest [interstitial lung disease/pneumonitis-like events, and QTc prolongation events]).

### **Statistical methods**

As the objective of the study is to collect physician-reported real world efficacy and safety data while offering access to AZD9291 to patients with significant unmet medical need, a total pre-defined recruitment target of treated patients is not applicable for this study.

All data will be presented for the overall full analysis set, and also by cohorts defined by number and type of previous treatment lines for the advanced disease. Descriptive statistics will be used for all variables, as appropriate. Continuous variables will be summarised by the number of observations, mean, standard deviation, median, minimum, and maximum. Categorical variables will be summarised by frequency counts and percentages for each category. OS, time to treatment discontinuation (TTD) and progression-free survival (PFS) will be summarized using Kaplan-Meier estimates of the median event time and quartiles together with their 95% confidence intervals.

TABLE OF CONTENTS	PAGE
PROTOCOL SYNOPSIS .....	2
TABLE OF CONTENTS .....	5
LIST OF ABBREVIATIONS AND DEFINITION OF TERMS.....	8
1. INTRODUCTION .....	10
1.1 Current non-small cell lung cancer (NSCLC)-related treatment patterns .....	10
1.2 Background and rationale for AZD9291 .....	11
1.3 Rationale for dose selection .....	11
1.4 Benefit/risk and ethical assessment.....	12
1.4.1 Nonclinical data .....	12
1.4.2 Clinical data .....	12
1.4.2.1 Study D5160C00005.....	13
1.4.2.2 Study D5160C00001 .....	14
1.4.2.3 Study D5160C00002.....	15
1.4.2.4 Study D5160C00003.....	15
1.4.3 Conclusions.....	15
2. STUDY OBJECTIVE .....	17
3. PATIENT SELECTION .....	17
3.1 Inclusion criteria .....	17
3.2 Exclusion criteria .....	18
4. STUDY CONDUCT .....	19
4.1 Study Plan .....	19
4.2 Restrictions .....	23
4.3 Discontinuation from study treatment .....	24
4.3.1 Procedures for discontinuation of a subject from study treatment.....	25
4.4 Patient Withdrawal or Study Termination .....	25
5. STUDY MEASURES .....	26
6. SAFETY REPORTING AND MEDICAL MANAGEMENT .....	28
6.1 Definition of adverse events .....	28
6.2 Definition of serious adverse events .....	28
6.2.1 Handling of deaths .....	29
6.2.2 Hy's Law.....	30

6.3	Reporting of serious adverse events.....	30
6.4	Overdose .....	30
6.5	Pregnancy.....	31
6.5.1	Maternal exposure.....	31
6.5.2	Paternal exposure .....	31
6.6	Management of toxicities related to AZD9291.....	32
6.6.1	Pulmonary Symptoms.....	32

## LIST OF ABBREVIATIONS AND DEFINITION OF TERMS

The following abbreviations and special terms are used in this Study Protocol.

Abbreviation or special term	Explanation
AE	Adverse event
AESI	Adverse Event of Special Interest
AZ	AstraZeneca
CI	Confidence Interval
CNS	Central nervous system
CRF	Case Report Form (electronic/paper)
CTCAE	Common Terminology Criteria for Adverse Event
CYP	Cytochrome P450
CT	Computer Tomography
DCO	Data cut-off
DLT	Dose limiting toxicity
ECG	Electrocardiogram
EGFR	Epidermal Growth Factor Receptor
EGFRm	EGFR Mutation positive; EGFR Sensitizing Mutation positive
GCP	Good Clinical Practice
GMP	Good Manufacturing Practice
IB	Investigator's Brochure
ICF	Informed Consent Form
ICH	International Conference on Harmonisation
ILD	Interstitial Lung Disease
ICMJE	International Committee of Medical Journal Editors
IP	Investigational Product
IVRS/IWRS	Interactive Voice Response System/ Interactive Web Response System
MedDRA	Medical Dictionary for Regulatory Activities
MRI	Magnetic Resonance Imaging
NSCLC	Non-Small Cell Lung Cancer
ORR	Objective response rate

Abbreviation or special term	Explanation
OS	Overall Survival
PFS	Progression Free Survival
PT	Preferred Term
QT	Interval on the electrocardiogram representing the duration of depolarization and repolarization of the heart
QTc	The QT interval corrected for heart rate
QTcF	QT interval corrected per Fredericia's formula
RECIST 1.1	Response Evaluation Criteria in Solid Tumors version 1.1
SAE	Serious adverse event
SOC	System Organ Class
SmPC	Summary of Product Characteristics
T790M	An amino acid substitution at position 790 in EGFR, from a Threonine (T) to a Methionine (M). Presence of T790M
TKI	Tyrosine Kinase Inhibitor
TTD	Time to treatment discontinuation
US	United States
WBDC	Web based data capture
WHO	World Health Organization

## 1. INTRODUCTION

### 1.1 Current non-small cell lung cancer (NSCLC)-related treatment patterns

Lung cancer has been the most common cancer in the world for several decades, and by 2012, there were an estimated 1.8 million new cases, representing 12.9% of all new cancers. It was also the most common cause of death from cancer, with 1.59 million deaths (19.4% of the total) ([GLOBOCAN 2012](#)). Non-small Cell Lung Cancer (NSCLC) represents approximately 80% to 85% of all lung cancers. At the time of diagnosis approximately 70% of patients with NSCLC already have locally advanced or metastatic disease not amenable to surgical resection. Patients presenting with unselected advanced NSCLC have a median overall survival (OS) of 10 to 12 months ([Bonomi 2010](#)).

The development of epidermal growth factor receptor (EGFR)-targeted tyrosine kinase inhibitors (TKI) have led to significant advances in patients with tumours harbouring EGFR mutations (EGFRm). Such types of mutations are seen in 10 to 15% of patients with NSCLC in the Western world and 30 to 40% in Asia. As a result of first-line studies comparing a TKI versus chemotherapy in EGFRm patients (IRESSA Pan-Asia Study [IPASS] and EUROpean TARceva versus Chemotherapy [[Mok et al 2009a](#), [Rosell et al 2012](#)]), the National Comprehensive Cancer Network (NCCN) and the European Society of Medical Oncology (ESMO) currently recommend treatment with an EGFR-TKI (e.g., erlotinib, gefitinib, or afatinib) in the front-line setting for those patients with documented EGFRm.

In patients with sensitizing mutations of EGFR, response rates of 50 to 80% have been reported with first-line TKI treatment, compared with less than 30% with conventional chemotherapy. Patients ultimately develop acquired resistance to these agents with progression of disease after approximately 9 to 13 months ([Engelman et al 2008](#), [Pao et al 2005](#), [Nguyen et al 2009](#), [Mok et al 2009b](#), [Rosell et al 2012](#)).

For patients whose tumors have progressed after treatment with an EGFR-TKI, the median OS rate is up to 2 years ([Wang et al 2012](#), [Wu et al 2010](#), [Fukuoka et al 2011](#)). Although EGFR-TKI (e.g., erlotinib, afatinib, gefitinib) are established therapies for patients with NSCLC known to have sensitising mutations in EGFR, the emergence of T790M mutation in patients treated with an EGFR-TKI agent has been described as the major route of development of resistance to this class of therapy ([Pao et al 2005](#), [Kobayashi et al 2005](#), [Yu et al 2013](#)).

There is no global standard of care for later lines of therapy after failure of both EGFR-TKI therapy and chemotherapy; current treatment options for this selected patient population are generally limited to chemotherapy or clinical trials ([Langer et al 2012](#)). No targeted therapy is currently approved for this specific disease setting.

Re-treatment with an EGFR-TKI (eg, switching to erlotinib following failure of gefitinib) confers response rates of around 10% and median progression-free survival (PFS) of 1.7 to

6.2 months (Lee et al 2013, Watanabe et al 2011). Afatinib, a second-generation EGFR-TKI, has shown similar efficacy (LUX-Lung 1 trial; Miller et al 2012), with a 7% response rate, 2-month improvement over placebo in PFS (median 3.3 versus 1.1 months) and no OS benefit shown; a similar 8% response rate and 4.4 months PFS was seen in the LUX-Lung 4 trial (Katakami et al 2013).

Second-line platinum-based chemotherapy post EGFR-TKI for EGFRm NSCLC generally provides response rates in the range of 20 to 30% (Gridelli et al 2012, Goldberg et al 2012, Maemondo et al 2010, Wang et al 2012, Wu et al 2010).

